- unexpected physiological response of the patient is not by itself considered a use error. A malfunction of a
- medical device that causes an unexpected result is not considered a use error. (ISO 14155:2020)
- **6.2.2 Reportable Adverse Events**
- 558 For this protocol, a reportable adverse event includes any untoward medical occurrence that meets one of 559 the following criteria:
- 560 1. An SAE as defined in section 6.2.1
- 561 2. An ADE, unless excluded from reporting in section 6.3
- 562 3. An AE as defined in section 6.2.1 occurring in association with a study procedure
- 4. An AE as defined in which leads to temporary or permanent discontinuation of a study device

- 5. An AE as defined in section 6.2.1 that affects the participant's ability to complete any study 565 procedures
- 566 6. An AE as defined in section 6.2.1 for which a visit is made to a hospital emergency department
- 567 7. Hypoglycemia meeting the reporting criteria in section 6.2.3
- 568 8. Hyperglycemia meeting the reporting criteria in section 6.2.4
- An AE as defined in section 6.2.1 considered to be related to either ineffective insulin (e.g.,
  insulin exposed to high temperature that loses potency), signs or symptoms related to insulin
  infusion, or changing of type of insulin related to an AE.
- Hypoglycemia and hyperglycemia not meeting the criteria below will not be recorded as adverse events.
  Skin reactions from sensor placement are only reportable if severe and/or required treatment.
- 574 All reportable AEs—whether volunteered by the participant, discovered by study personnel during
- 575 questioning, or detected through physical examination, laboratory test, or other means—will be reported
- 576 on an AE CRF online. Each AE CRF is reviewed by the Medical Monitor to assess safety and to verify
- 577 the coding and the reporting that is required.

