# 578 **6.2.3 Hypoglycemic Events**

- 579 Hypoglycemia is only reportable as an adverse event when one of the following criteria is met:
- A hypoglycemic event occurred meeting the following definition of severe hypoglycemia: the 580 event required assistance of another person due to altered consciousness, and required another 581 582 person to actively administer carbohydrate, glucagon, or other resuscitative actions. This means that the participant was impaired cognitively to the point that he/she was unable to treat 583 himself/herself, was unable to verbalize his/ her needs, was incoherent, disoriented, and/or 584 combative, or experienced seizure or loss of consciousness. These episodes may be associated 585 with sufficient neuroglycopenia to induce seizure or loss of consciousness. If glucose 586 measurements are not available during such an event, neurological recovery attributable to the 587 restoration of glucose to normal is considered sufficient evidence that the event was induced by a 588 low glucose concentration. 589
- Evaluation or treatment was obtained at a health care provider facility for an acute event
   involving hypoglycemia, or the participant contacted the site and received guidance following
   the occurrence of an acute event involving hypoglycemia
- Hypoglycemia occurred that was associated with an ADE as defined in section 6.2.1
- Study device discontinued due to hypoglycemia
- 595 When a severe hypoglycemia event occurs (as defined above), a Hypoglycemia CRF should be completed 596 in addition to the Adverse Event CRF. Severe hypoglycemia events should be considered serious adverse 597 events with respect to reporting requirements. When a severe hypoglycemia event occurs during use of a 598 study device, it generally will be considered unrelated to the device (per section 6.2.1) if the device
- functioned as intended and there does not appear to be a flaw in how the device is intended to function.
- 600 6.2.4 Hyperglycemic/Ketotic Events
- 601 Hyperglycemia or ketosis is only reportable as an adverse event when one of the following criteria is met:
- evaluation or treatment was obtained at a health care provider facility for an acute event involving
   hyperglycemia or ketosis, or the participant contacted the site and received guidance on how to
   manage the hyperglycemia/ketosis

- the event involved DKA, as defined by the Diabetes Control and Complications Trial (DCCT) and
   described below

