# 6.2.5 Relationship of Adverse Event to Study Device or Study Procedure

- The site investigator will assess the relationship of any adverse event to be related or unrelated by
- determining if there is a reasonable possibility that the adverse event may have been caused by the study
- 624 device or a study procedure. The Medical Monitor also will make this assessment, which may or may not
- agree with that of the site investigator. Reporting requirements will be based on the Medical Monitor's
- 626 assessment as the Sponsor's representative.
- To ensure consistency of adverse event causality assessments, investigators should apply the following general guideline when determining whether an adverse event is related:
- **Unrelated:** The AE is clearly not related to a study device/procedure and a likely alternative etiology exists such as an underlying disease, environmental or toxic factors or other therapy.
- Unlikely Related: The AE does not follow a reasonable temporal sequence during or after use of study device/procedure and a more likely alternative etiology exists such as an underlying disease, environmental or toxic factors, or other therapy.
- Possibly Related: The AE occurred in a reasonable time during or after use of study device or a study procedure; but could be related to another factor such as an underlying disease,
   environmental or toxic factors, or other therapy; and there is a possible, though weak, scientific basis for establishing a causal association between the AE and the study device.
- Probably Related: The AE occurred in a reasonable time during or after use of study device or a study procedure; is unlikely to be related to another factor such as an underlying disease, environmental or toxic factors, or other therapy; and there is a plausible, though not strong, scientific basis for establishing a causal association between the AE and the study device.
- Definitely Related: The AE occurred in a reasonable time during or after use of study device or a study procedure; cannot be explained by another factor such as an underlying disease, environmental or toxic factors, or therapy; and there is a strong scientific basis for establishing a causal association between the AE and the study device.

646 Events determined to be *Possibly Related*, *Probably Related*, or *Definitely Related* will be considered to

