# 700 **6.3 Reportable Device Issues**

All UADEs and ADEs as defined in section 6.2.1 will be reported on both a Device Issue CRF and AE CRF, except for skin reactions from CGM sensor placement or pump infusion set placement that do not

703 require pharmacologic treatment.

Device complaints and device malfunctions will be reported except in the following circumstances. These
 occurrences are expected and will not be reported on a Device Issue CRF assuming criteria for a UADE
 or ADE have not been met:

- CGM sensor lasting fewer days than expected per manufacturer
- CGM tape adherence issues
- Pump infusion set insertion lasting fewer days than expected per manufacturer
- Battery lifespan deficiency due to inadequate charging or extensive wireless communication
- Intermittent device component disconnections/communication failures not requiring system
   replacement or workaround/resolution not specified in user guide/manual.
- Device issues clearly addressed in the user guide manual that do not require additional troubleshooting

715 Use error (as defined above) will only be reported on a device issue form if an Adverse Event results from 716 the error. In these cases, both a Device Issue and an Adverse Event form will be completed.

717 **6.4 Timing of Event Reporting** 

SAEs possibly related to a study device or procedure and UADEs must be reported by the investigator to the Sponsor within twenty-four (24) hours of the site becoming aware of the event. This can occur via phone or email, or by completion of the AE CRF and Device Issue CRF if applicable. If the AE CRF is not initially completed, it should be completed as soon as possible after there is sufficient information to evaluate the event. All other reportable ADEs and other reportable AEs should be submitted by completion on the respective CRF within seven (7) days of the site becoming aware of the event.

The Sponsor will notify all participating investigators of any adverse event that is serious, related, and unexpected. Notification will be made within ten (10) working days after the Sponsor becomes aware of the event.

- Each site principal investigator is responsible for reporting serious study-related adverse events and
- abiding by any other reporting requirements specific to his/her Institutional Review Board or Ethics
- 729 Committee. Where the JCHR IRB is the overseeing IRB, sites must report all serious, related adverse
- rain events within seven calendar days.

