# 743 **6.5 Safety Oversight**

The study Medical Monitor will review all adverse events and adverse device events that are reported

during the study. SAEs typically will be reviewed within twenty-four (24) hours of reporting. Other AEs

typically will be reviewed on a weekly basis. Additionally, the Medical Monitor will review compiled

safety data at periodic intervals (generally timed to the review of compiled safety data by the DSMB).

- 748 The Protocol Chair/Coordinating Investigator will be informed of all cases of severe hypoglycemia and
- 749 DKA and the Medical Monitor's assessment of relationship to the study device; and informed of all 750 reported device issues.
- A Data and Safety Monitoring Board (DSMB) will be informed of all cases of severe hypoglycemia and
- diabetic ketoacidosis irrespective of device relationship, all device-related SAEs, and all UADEs at the
- time that they occur during the study and will review compiled safety data at periodic intervals. The

DSMB also will be informed of any ADEs not meeting criteria for a UADE if the Medical Monitor

requests the DSMB review. The DSMB can request modifications to the study protocol or suspension or

outright stoppage of the study if deemed necessary based on the totality of safety data available. Details

- regarding DSMB review will be documented in a separate DSMB document.
- 758 **6.6 Stopping Criteria**

# 759

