# 6.6.1 Participant Discontinuation of Study Device

In the case of an unanticipated system malfunction resulting in a severe hypoglycemia or DKA event (or a

- malfunction that could have led to severe hypoglycemia or DKA), use of the study device will be
- suspended while the problem is diagnosed. The UADE will be reported to the IRB, DSMB, and FDA.
- After assessment of the problem and any correction, use of the study device will not be restarted until approval is received from the IPP DSMP and EDA
- approval is received from the IRB, DSMB, and FDA.
- In the absence of a device malfunction, use of the study device by a participant will be discontinued if any
   of the following occur and the participant will be withdrawn from the study:
- The investigator believes it is unsafe for the participant to continue on the intervention. *This could be due to the development of a new medical condition or worsening of an existing condition; or participant behavior contrary to the indications for use of the device that imposes on the participant's safety*

- The participant requests that the treatment be stopped
- Two distinct episodes of DKA as defined in section 6.2.4
- Two distinct severe hypoglycemia events as defined in section 6.2.3
- One episode of DKA as defined in section 6.2.4 and one severe hypoglycemia event as defined in section 6.2.3

Each DKA or severe hypoglycemia event will be reviewed by the Medical Monitor and by the DSMB

with respect to determination of cause and whether the occurrence of the event can be attributed to use of the study device.

An additional requirement for continued study device use following a single DKA or severe

780 hypoglycemia event will be that the site investigator believes that the event is unlikely to recur and that it

is safe for the participant to continue to use the system. Additionally, if either the Medical Monitor or

- DSMB determines that the occurrence of the event indicates that it is not safe for the participant to
- continue to use the study device, use will be discontinued.

786

Even if the study device system is discontinued, the participant will be encouraged to remain in the study through the final study visit.

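### Section 6.4 allows seven days to report severe hypoglycemia or DKA judged unrelated, so the section 6.5 commitment to tell the DSMB of every such event as it occurs cannot be assured

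*Protocol*

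**What the plan says.** **Site-to-Sponsor clock (protocol 6.4).** The fast route is limited by causality: "SAEs possibly related to a study device or procedure and UADEs must be reported by the investigator to the Sponsor within twenty-four (24) hours" of site awareness. For the rest, "All other reportable ADEs and other reportable AEs should be submitted by completion on the respective CRF within seven (7) days" of awareness. Item 1 of the reportable list in 6.2.2 is "An SAE as defined in section 6.2.1", with no condition on relatedness. A serious event that is neither possibly related nor a UADE therefore falls in the seven-day class; no other limit is printed for it.

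**Status of the two key events (6.2.3, 6.2.4).** "Severe hypoglycemia events should be considered serious adverse" events for reporting purposes, and the same is said of DKA. Both sections add that an event during device use will generally be classed as unrelated to the device if the device worked as intended and its intended function shows no apparent flaw.

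**Whose opinion counts (6.2.5, 6.2.8).** The Medical Monitor also assesses relatedness and may or may not "agree with that of the site investigator. Reporting requirements will be based on the Medical Monitor's" assessment. Section 6.2.8 gives the Monitor the final say on causality.

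**Oversight (6.5).** The DSMB is to be told of all severe hypoglycemia and "diabetic ketoacidosis irrespective of device relationship, all device-related SAEs, and all UADEs at the" time of occurrence. The Medical Monitor typically reviews SAEs within 24 hours, counted from reporting.

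**Continued use (6.6.1).** Without a malfunction, a child may continue after a single event if the site investigator thinks recurrence unlikely and use safe. Use ends if the Medical Monitor or "DSMB determines that the occurrence of the event indicates that it is not safe for the participant to" go on using the device.

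The SAP does not address reporting times.

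**The concern.** Section 6.5 drops relatedness as a condition for DSMB notice of severe hypoglycemia and DKA. Section 6.4 keeps it as the condition for fast reporting by the site. The step that feeds the DSMB is thus slower than the notice it must support, and it is slow for the class into which 6.2.3 and 6.2.4 generally place these events.

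Severe hypoglycemia and DKA are key clinical safety events in children aged 2 to under 6. Section 1.4 calls the settings algorithm experimental, and section 4.1 names the portal that produces the recommendations as an investigational component. Section 8.18 has the DSMB review safety data with no formal stopping rules, so event-by-event notice carries much of the independent oversight. If notice is late, the child may receive another AI-driven change before anyone outside the site has considered the event.

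**Working it through.** The documents derive no figure on this point, so there is none to reproduce. The check has two parts.

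**1. The clauses side by side**

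- A severe hypoglycemia or DKA event occurs, and the portal, pump and CGM all worked as designed.
- The site applies 6.2.3 or 6.2.4 and generally calls it unrelated. On the 6.2.5 scale, unrelated and unlikely related both fall below the reasonable-possibility standard.
- The 24-hour condition in 6.4 is not met, so the site has seven days.
- The Medical Monitor could overrule the site under 6.2.5 and 6.2.8, but only after receiving the report. In practice the site's first opinion sets the clock.
- The Monitor's 24 hours start at reporting, so they do not shorten the site's interval.
- The DSMB notice in 6.5 depends on the same report.
- Section 6.6.1 suspends use during diagnosis only for an unanticipated system malfunction. Otherwise nothing holds use or settings changes until central review.

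**2. How often a settings change can come first**

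Inputs:

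- Scheduled AI changes at nominal days 3, 7, 14, 28 and 42 (protocol summary, Table 1, Table 4-1).
- Treatment period of 8 × 7 = 56 days.
- Site limit of 7 days or 1 day (6.4), and Medical Monitor review of 1 day (6.5).
- Assumptions: the site learns of the event the day it happens, uses its full limit, and visits fall on their nominal days.

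Rule: for an event at time t and total lag L, a change at visit v comes first if t < v ≤ t + L. For each L, count the part of days 0 to 56 on which at least one visit qualifies.

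- L = 7 (report due): days 0–14, 21–28 and 35–42, so 14 + 7 + 7 = 28 of 56 (50.0%).
- L = 7 + 1 = 8 (Monitor review done): days 0–14, 20–28 and 34–42, so 14 + 8 + 8 = 30 of 56 (53.6%).
- L = 1 (report due under a 24-hour limit): one day before each of five visits, so 5 × 1 = 5 of 56 (8.9%).
- L = 1 + 1 = 2 (Monitor review under a 24-hour limit): 5 × 2 = 10 of 56 (17.9%).

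Two changes can come first for events in the first 3 days at L = 7, and on 4 of the 56 days at L = 8.

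Example: for an event on day 1, the report is due by day 8 and review by about day 9. The 3-day visit (days 2–4) and the 1-week visit (days 5–9) can both come first.

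Sensitivity: with visits drawn uniformly within their Table 4-1 windows (2,000 draws), the share ranged over 46–54% at L = 7, 48–57% at L = 8 and 16–18% at L = 2. Off-cycle optimizations under 3.3.4 are not counted and could only add.

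**The case against.** **Only one clause conflicts.** A reader might infer that 6.6.1 sets a time that is missed. It states none. The Medical Monitor's 24 hours run from reporting and can be met whatever the site does. Only the DSMB clause in 6.5 conflicts with 6.4. That clause gives no hour or day limit and could be read as event-by-event rather than batched notice. Details are deferred to a separate DSMB document that is not available here. This stands, and the point is confined accordingly. It does not remove the conflict: up to seven days before the Sponsor knows is hard to square with notice when the event occurs, and 6.4 as printed still sets the site's limit.

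**Safety review is not bypassed.** A reader might infer that a child's settings can change with nobody having considered the event. The documents do not support that. Adverse events are assessed at each visit, a study physician reviews each recommended setting before it goes on the pump (3.3.1, 3.3.2), the investigator may override it, and 6.6.1 makes continued use depend on the investigator's judgement. This also stands. These checks are local, however, and none has to wait for central review.

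**The fast route already catches the most worrying events.** UADEs and anything at least possibly related have 24 hours, and 6.2.5 sets that threshold low. This partly stands, but the statements in 6.2.3 and 6.2.4 steer properly functioning-device events away from that category.

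**The counts are a ceiling.** Seven days is a maximum, and sites may report sooner. No severe hypoglycemia or DKA rate is given, so 30 of 56 is not a probability that a child is affected, and eight days as a share of the treatment period measures no exposure.

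**The remedy is partial.** Ten of 56 days remain. If the site first hears of an event at a scheduled visit, a change at that visit precedes central review under either limit. This stands.

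**Conclusion.** The point holds as a contradiction within the protocol. Section 6.4 permits up to seven days for severe hypoglycemia or DKA judged not related, the general default when the device functioned as intended. Section 6.5 commits to DSMB notice of all such events as they occur, irrespective of device relationship. Sections 6.2.5 and 6.2.8 do not close the gap, because the Medical Monitor can assess only what has been sent.

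The consequence is that independent central review can follow a further AI settings change. On the nominal schedule this applies to events on 30 of 56 days, against 10 of 56 with a 24-hour limit. Both figures assume same-day site awareness, full use of the site's limit and 24 hours for Medical Monitor review. They describe what the text allows, not how often it will happen.

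**What to change.** In section 6.4, require every severe hypoglycemia and every DKA event to be reported to the Sponsor within 24 hours of site awareness, whatever the site's opinion on relatedness, by the phone, email or CRF route already given there. State that relatedness governs onward reporting to the IRB, FDA and other investigators, not this clock. Align the wording of 6.5 so that DSMB notice is tied to the Sponsor's receipt of the report.

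Extending the 24-hour limit to every SAE is optional; the contradiction does not require it.

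The cost is a short change to 6.4 and a matching edit in 6.5. Sites complete the same forms, or make a phone call or send an email, sooner for these events. No treatment, settings or stopping rule changes. The interval before central review is shortened, not removed.

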# 743 **6.5 Safety Oversight**

The study Medical Monitor will review all adverse events and adverse device events that are reported

during the study. SAEs typically will be reviewed within twenty-four (24) hours of reporting. Other AEs

typically will be reviewed on a weekly basis. Additionally, the Medical Monitor will review compiled

safety data at periodic intervals (generally timed to the review of compiled safety data by the DSMB).

- 748 The Protocol Chair/Coordinating Investigator will be informed of all cases of severe hypoglycemia and
- 749 DKA and the Medical Monitor's assessment of relationship to the study device; and informed of all 750 reported device issues.
- A Data and Safety Monitoring Board (DSMB) will be informed of all cases of severe hypoglycemia and
- diabetic ketoacidosis irrespective of device relationship, all device-related SAEs, and all UADEs at the
- time that they occur during the study and will review compiled safety data at periodic intervals. The

DSMB also will be informed of any ADEs not meeting criteria for a UADE if the Medical Monitor

requests the DSMB review. The DSMB can request modifications to the study protocol or suspension or

outright stoppage of the study if deemed necessary based on the totality of safety data available. Details

- regarding DSMB review will be documented in a separate DSMB document.
- 758 **6.6 Stopping Criteria**

# 759

# 6.6.1 Participant Discontinuation of Study Device

In the case of an unanticipated system malfunction resulting in a severe hypoglycemia or DKA event (or a

- malfunction that could have led to severe hypoglycemia or DKA), use of the study device will be
- suspended while the problem is diagnosed. The UADE will be reported to the IRB, DSMB, and FDA.
- After assessment of the problem and any correction, use of the study device will not be restarted until approval is received from the IPP DSMP and EDA
- approval is received from the IRB, DSMB, and FDA.
- In the absence of a device malfunction, use of the study device by a participant will be discontinued if any
   of the following occur and the participant will be withdrawn from the study:
- The investigator believes it is unsafe for the participant to continue on the intervention. *This could be due to the development of a new medical condition or worsening of an existing condition; or participant behavior contrary to the indications for use of the device that imposes on the participant's safety*

- The participant requests that the treatment be stopped
- Two distinct episodes of DKA as defined in section 6.2.4
- Two distinct severe hypoglycemia events as defined in section 6.2.3
- One episode of DKA as defined in section 6.2.4 and one severe hypoglycemia event as defined in section 6.2.3

Each DKA or severe hypoglycemia event will be reviewed by the Medical Monitor and by the DSMB

with respect to determination of cause and whether the occurrence of the event can be attributed to use of the study device.

An additional requirement for continued study device use following a single DKA or severe

780 hypoglycemia event will be that the site investigator believes that the event is unlikely to recur and that it

is safe for the participant to continue to use the system. Additionally, if either the Medical Monitor or

- DSMB determines that the occurrence of the event indicates that it is not safe for the participant to
- continue to use the study device, use will be discontinued.

786

Even if the study device system is discontinued, the participant will be encouraged to remain in the study through the final study visit.

